1. ANTIBIOTIC REGIMENS AND NEONATAL MANAGEMENT

Maternal antibiotics

Antibiotic regimen for prevention of vertical GBS transmission

In maternity units using either risk factor or rapid test based screening, the IAP regimen will be identical. IAP should be administered as soon as possible after the decision is made and the woman has given assent. Intravenous benzylpenicillin (3 grams) should be infused and an additional 1.5 grams of intravenous penicillin given every four hours until delivery. In those women who are allergic to penicillin, 900mg of Clindamycin should be administered intravenously every eight hours, until delivery.

Antibiotics for maternal infection

If a woman is pyrexic or is suspected or confirmed to have chorioamniotitis, broad spectrum antibiotics (e.g. fourth generation cephalosporins) should be given immediately.

Collection of maternal antibiotic data

The offer and prescription of IAP or any other antibiotics for maternal infection will be recorded on the GBS2 checklist, alongside details of date and time of first dose, dosage and number of subsequent doses.

Neonatal Management

Management of well infants at risk of early onset sepsis

Well infants born to women who had one risk factor for GBS transmission during labour should be monitored hourly for the first two hours after birth, then at two hourly intervals until 12 hours after birth, with assessment made of their general wellbeing, heart rate, respiratory rate and temperature. Clinical judgement should be used to determine whether the appearance of one clinical indicator of potential sepsis necessitates further investigations and administration of antibiotics.

Regardless of the status of the infant, if intravenous antibiotics were administered to the mother for confirmed or suspected invasive bacterial infection e.g. sepsis at any time during labour or in the 24 hours before or after birth, the baby should be evaluated and antibiotic treatment started immediately, before the test results are available if necessary.

Collection of neonatal antibiotic data

The prescription of antibiotics for neonatal infection will be recorded on the GBS2 checklist, with details of date and time of first dose, dosage and number of subsequent doses.

Management of infants with clinical signs of EOGBS disease

Many infants with EOGBS disease will have signs at or soon after birth. Whilst initially subtle these can progress quickly.[31] Respiratory distress, seizures and signs of shock are particularly important indicators for treatment. Whether the mother

Version 1.0 22nd December 2015 GBS2 Page 39 of 81

received IAP or not, clinical acumen should be used to determine if any baby with clinical signs and symptoms of sepsis should be administered antibiotics immediately, or if investigations should be undertaken before the start of antibiotic administration. If investigations are undertaken then these should include a blood culture to measure the level of C-reactive protein. A lumbar puncture to obtain cerebrospinal fluid should be undertaken if thought safe and timely, and there is a strong clinical suspicion of infection with or without symptoms or signs of meningitis.

Urine microscopy or culture, and skin culture, unless there are localised signs of infection, are not indicated.

Intravenous benzylpencillin with gentamycin is the first choice antibiotic regimen for empirical treatment of suspected infection. The suggested starting dose of benzylpencillin is 25mg kg⁻¹ every 12 hours. The suggested starting dose of gentamycin is 5mg kg⁻¹, with further doses as required.[47] Clinicians should manage the situation according to the NICE Guidelines on early onset neonatal infection and their local policies, with the engagement of clinical microbiologists or infectious disease doctors with specific experience in neonatal infection.

In multiple births where one sibling has suspected or confirmed EOGBS disease, the other siblings should be considered at high risk, evaluated and treated with antibiotics.

Collection of neonatal treatment and outcome information

Information on the immediate destination of the baby, the date of discharge, any signs and symptoms of infection, and any antibiotic used will be collected from the neonatal notes using dedicated data collection forms and transcribed to a trial specific database by the research midwife. The unique trial number will be used to link the information from the baby with that obtained from its mother.

After the study period

The rapid test screening units will have the GeneXpert system and any remaining test kits retrieved by the study team, and will revert to their previous clinical policy for screening for GBS.

Schedule of Assessment (in Diagrammatic Format)

Assessment	Screening	On-study treatment phase	End of Study	Follow up visits
Risk factor associated with GBS colonisation	x			

End of Study Definition

The main study will be deemed complete once all babies born to mothers in the study have reached six months of age.

The sub-study will be deemed complete when the last woman in the last maternity unit has delivered and her baby has reached 12 weeks of age. This will ensure that sufficient time has passed for any follow-up faecal samples to be received in the central microbiology laboratories at Bart's Health NHS Trust.

STATISTICAL CONSIDERATIONS

Test accuracy study

The sample size of the test accuracy study is dependent on the sensitivity of the rapid test. For the test to be proven useful we need to show that it will detect a higher proportion of GBS infections than other tests, but not at the cost of low specificity and/or unnecessary administration of IAP.

Results from GBS1 suggested that the most cost-effective test (if untargeted universal IAP was excluded) was antenatal culture for GBS at 35-37 weeks' gestation. In GBS1 the sensitivity of this test was 75.8% (95% CI 47.2% to 91.5%). Thus if we could prove that the sensitivity of rapid test was higher than 90% the results of the GBS2 study would be convincing. This is a stringent test — a lower threshold might also be adequate. We will not be comparing the rapid test with antenatal GBS culture testing within the study, but comparing with this result from external literature. Thus we will be undertaking a "one sample, sample size" computation comparing against a fixed value.

We have data from a systematic review on the performance of the new GBS test. From the meta-analysis of 9 studies, the pooled accuracy of the test was estimated, giving a sensitivity of 96.4% (90.8-98.6) and specificity of 98.9% (97.5-99.5). Sample size calculations are thus based on showing a test with sensitivity of 96.4% is greater than a fixed value of 90%. With a power of 90% to demonstrate this sensitivity, 167 cases of maternal GBS colonisation are required (or 136 at 80% power).

A sample size of 676 would provide 90% chance of us accruing enough GBS colonised women to have 90% power to show the sensitivity of the GBS test to be statistically significantly (with p<0.05) greater than 90% should the meta-analytical estimate of its performance (96.4%) be correct whilst allowing for 10% loss from failed tests, based on the GBS prevalence observed in GBS1, which was 29.8% (89/299, 95% CI: 24.6%-35.2%). Of the 606 participants with data we would expect 167 to be GBS carriers and 439 to be negative for GBS colonisation. If the prevalence of GBS colonisation is actually at the lower 95% confidence interval from GBS1, namely 24.6%, then 673 total women will give 90% chance of observing 136 cases of GBS colonisation, including 10% lost tests.

The 95% Cis we would observe on sensitivities and specificities of 85%, 90%, 95% and 98% with a sample size of 676 (606 with data) are shown in **Table 1** and have adequate precision (sensitivity within 10%, specificity within 6%) for modelling.

Point estimate	CI for sensitivity (n = 167)	CI for specificity ($n = 439$)
85	78.7 – 90.1	81.3 – 88.2
90	84.2 – 94.0	86.8 – 92.7
95	90.9 – 97.9	92.5 – 96.8
98	94.8 – 99.6	96.2 – 99.1

Table 1: Confidence Intervals for sensitivity and specificity at various point estimates Cluster

randomised trial

The focus of this sample size calculation is on the effectiveness of the rapid GBS test within a cluster randomised trial (CRT) in which the number of clusters, in this case maternity units, is limited by the by the willingness of NHS Trusts to participate, but the number of potential participants is only limited by the duration of study period.

The CRT requires a minimum of 8 maternity units per screening strategy i.e. a total 16 units. Based on assumptions cited below, we estimate that the sample size per cluster will be approximately 83. This equates to a total sample size of approximately 664 participants per arm, and so therefore allows sufficient numbers of women to be recruited for the test accuracy study too.

As there are two arms (Standard Practice / Rapid Test), each of at least 664 participants this gives a projected sample size of 1,328 women. This has been rounded up to a target sample size of 1,340 women.

For the sub-study looking at antibiotic resistance, of the 1,340 study sample size, we estimate that around 650 will be recruited from centres in London and the South-East. Of these, 325 will be assigned to the rapid test arm. Assuming that one out of five women decline their invitation to participate in the sub study, we estimate that the total sample size will be around 260 participants.

The proportion of women receiving IAP for prevention of GBS transmission under a risk factor based strategy is expected to be in the region of 50% to 75%. In GBS1, only 47% of women with risk factors received IAP. We expect that greater understanding and implementation of the RCOG and NICE guidelines will have improved this figure in contemporary practice, but it is unlikely that there will be perfect compliance with RCOG/ NICE guidelines. We thus estimate an IAP rate of 75% to be reasonable. This primary outcome is a process outcome and so the within-cluster correlation of this outcome (the ICC) is expected to be higher than it would be for a clinical outcome. We have therefore considered the sensitivity of our

calculations to a range of proportions in the risk factor-based screening strategy group and a range of ICC values which we believe to be quite conservative. All of our calculations allow for 90% power and 5% significance.

Guided by the need to have at least 676 women to fulfil the needs of the test accuracy study, and under a range of values for the risk-factor based strategy IAP rates and values of ICC, we have worked out the difference detectable and equivalent relative risk reduction (RRR), shown in **Table 2**.

IAP rate in risk- factor screening strategy	ICC=0.2	ICC = 0.1	ICC = 0.05	ICC = 0.01
75	38% (RR = 0.51)	48% (RR = 0.64)	55% (RR = 0.73)	63% (RR = 0.84)
60	22% (RR = 0.37)	32% (RR = 0.53)	39% (RR = 0.65)	47% (RR = 0.78)

Table 2: Range of relative risk reductions achieved with a range of important parameters

The CRT would have around 90% power to detect a reduction in the proportion of women prescribed antibiotics from 75% to 63% (RRR of about 20%) for a low value of the ICC; to a reduction from 75% to 38% for a very conservative value of the ICC (0.2), equating to a relative risk reduction of 50%.

We have not acknowledged varying cluster sizes in our calculations, as we consider the coefficient of variation of unit delivery sizes to be small (approximately 0.21 based on annual delivery rates for 2013) and can be altered by varying the study duration at maternity units. Given our conservative assumptions, and that the impact of the rapid test on the rate of IAP provided is expected to be large, it is expected that the impact of any varying cluster sizes will be minimal.

Analysis methods

Test accuracy study

The accuracy of the rapid test for detection of GBS colonisation will be expressed as sensitivity, specificity, positive and negative predictive values, and positive and negative likelihood ratios, along with their associated 95% confidence intervals.

Cluster randomised trial

The baseline characteristics, for example parity, ethnicity, risk factors and gestational age at onset of labour will be summarised as means and standard deviations, or medians and inter-quartile ranges, grouped by unit allocation (risk factor based screening or rapid test based screening).

Analyses of outcomes will be by intention to treat. As randomisation will be at the maternity unit level, appropriate statistical methods to account for the clustering within units will be used in the analysis.

The primary aim of the study is to evaluate whether the proportion of women prescribed IAP for prevention of GBS transmission differs between the screening strategy groups. In statistical terms the null-hypothesis, that of no difference can be tested using a mixed logistic regression model with prescription of IAP as the dependent variable, study screening strategy group as the independent variable, and maternity unit as a grouping (random effect) variable. These models will be fitted using population averaged models (similar to multilevel models) using GEE methods in STATA. Population averaged models, as opposed to random effects models, will be used as within the framework of cluster randomised trials: random effects models both lack appropriate interpretation and might be biased.[52] Similar models will be fitted for secondary outcomes and appropriate link functions used for outcomes which are not binary.

Primary analysis will be unadjusted, but secondary analyses will adjust for prespecified and clinically important baseline covariates. These will include gestational age, and presence of individual risk factors, and maternity unit level covariates such as size. We will allow for clustering at the maternity unit level. The primary analysis will be a complete case analysis. However, missing data will be reported and associations between outcomes explored. Depending on the nature of these associations and the extent of the missing data, sensitivity will be explored by means of multiple-imputation.

The primary outcome will be considered significant at the 5% level (and so the 95% Cis reported); whereas other secondary outcomes will be interpreted cautiously as the CRT is not necessarily powered to detect a difference in these. Reports of interim analysis will be supplied in confidence to the DMEC during the recruitment period. Final analysis will be performed once all babies born to mothers in the study have reached six months of age.

Relatedness sub-study

The proportions of mothers and infants carrying antibiotic resistant bacteria will be documented and the degree to which the strains are indistinguishable when characterised using techniques which include; matrix-assisted laser desorption ionization—time of flight mass spectrometry, antibiotic susceptibility profile, and genetic analyses (including analysis of resistance mechanisms) will be documented. These data will allow an estimate of the extent to which mothers and infants at around six weeks of post-natal life carry indistinguishable strains of resistant bacteria. This data will be used to inform the design of more detailed studies aimed at better understanding transmission pathways with the objective of defining potential interventions.

Accrual and study initiation roll-out

We will not attempt to start recruitment in all sites simultaneously but instead plan on opening equal numbers of control and experimental sites in staggered waves. The burden of supporting sites will be spread over 12 months and lessons learnt in the first wave will be carried forward to the management later units.

A conservative estimate of the number of eligible deliveries per 4 weeks in the participating Trusts indicates an average of 71 deliveries per site, so a study period of 4-5 weeks would be sufficient at all sites. We consider this period the minimum needed should a Trust be assigned a rapid test to implement its use as policy.

Economic analysis

Resource use data will be collected within GBS2 to estimate the costs associated with the diagnosis of women using the rapid test compared to risk factor alone based screening. The main resources to be monitored include:

- The resources required to perform the GeneXpert rapid test and act on its results
- Any resource use associated with identifying risk factors, and establishing they exist before acting on the result
- The administration of IAP and associated resource use (midwife time, monitoring patient)
- Monitoring, investigation and management of infants born to women exhibiting risk factors for GBS transmission
- Any extended stays on post-natal ward for neonatal monitoring and any admissions to neonatal unit (special, high or intensive care)

Estimates of the incidence of EOGBS disease, treatment effects of maternal antibiotics on EOGBS disease, and mortality rates will be based on secondary sources.[54]

Information on unit costs or prices will be obtained and assigned to each resource item in order that an overall cost per patient can be calculated. Cost data will be collected from two principle sources:

Firstly, the test accuracy study will provide resource use data to estimate costs incurred in administering the rapid test. Where possible cost data, such as cost of midwife time etc will be collected from routine sources, including those obtained from Curtis and Netten[55] and hospital finance departments. Many cost sources are already identified and available in recently published sources including a systematic

review and the GBS1 study.[56] These cost data will be appropriately updated by revisiting the relevant sources.

The overall approach to the economic analysis will take the form of a model based economic evaluation and will build on that used in GBS1,[44, 56] whilst maintaining all the alternative screening and treatment pathways. We will refine and develop the previous decision tree model using the data from GBS2 and from up-to-date secondary sources. The test accuracy study will provide data on sensitivity and specificity of the GeneXpert rapid test and allow the treatment pathways followed by women on the basis of the tests results to be modelled. The CRT will provide clear data on feasibility of the woman receiving antibiotics before the baby is delivered, and provide clarity for the treatment pathways based being compared in the study.

A decision based analytic model will be used to allow the extrapolation of cost and effectiveness parameters beyond the data observed in the clinical study (and to allow extrapolation to other settings, for example, an unselected population of women in labour).

A limitation in the economic model on which the GBS1 evaluation was based is that this was an accuracy only study. This meant that treatment pathways had to be modelled and could only suggest what the comparator pathway should look like on the basis of the test result. There was concern that, in reality, clinical practice was likely to be very heterogeneous compared to what our model assumed. The advantage of the GBS2 CRT is that it will provide absolute clarity on the comparators upon which the economic evaluation is based. Thus, the previous economic evaluation will be refined using GBS2 data and compared with many of the previously modeled alternatives and combinations.

The two main strategies compared in GBS2 will be i) screening based on the presence of risk factors, and ii) screening based on the results of the rapid test during labour. These strategies will be compared against each other and with a 'do nothing' strategy using many of the 'modelled' pathways utilized in the GBS1 study. Comparing the interventions to 'do nothing' will again require a calibration process, but as this is not a strategy used in clinical practice it is not included as an arm in the trial.

The data available from the GBS2 study will be patient-specific resource use and costs adjusted for clustering. Given the skewness inherent in most cost data and the concern of economic analyses with mean costs, we shall use a bootstrapping approach in order to calculate confidence intervals around the difference in mean costs. [57, 58].

Using data from GBS2 it will be possible to estimate the additional cost per case of IAP avoided. An incremental economic analysis will be conducted. The base-case analysis will be framed initially in terms of cost-consequences, reporting data in a disaggregated manner, adjusted for cluster, and report on the incremental cost, the

important consequences including use of IAP, alongside data on the number of true positive cases of GBS detected, etc.

The model based analysis will consider treatment over the total disease duration for an infected infant and will include appropriate consideration of medical and/or surgical treatments provided in the longer term, depending on availability of appropriate data. Dependent on data reported in published sources, the model-based analysis will adopt either a cost-effectiveness (i.e. cost per life year gained) or a cost-utility (i.e. cost per quality-adjusted life year [QALY]) approach. In GBS1, results were presented in terms of cost per episode of EOGBS disease avoided, and EOGBS associated infant death avoided, because there were insufficient data available to estimate a QALY based on infection with GBS. If QALY data are now available the results will be presented in terms of cost per QALY.

The model based analysis will allow projection of costs and benefits beyond the endpoint of the study which will be when the infant reaches six weeks age of age, to consider a lifetime impact. Given the relatively long time horizons being considered in these analyses, many of the costs (and benefits) will be incurred (and experienced) in future years. Using discounting, adjustments will be made to reflect this differential timing. The base-case analysis will follow recommendations of NICE and discount costs and benefits at 3.5%.

The results of these economic analyses will be presented using cost-effectiveness acceptability curves to reflect sampling variation and uncertainties in the appropriate threshold cost-effectiveness value. Both simple and probabilistic sensitivity analyses will be used to explore the robustness of these results to investigate plausible variations in key assumptions and variations in the analytical methods used, and to consider the broader issue of the generalisability of the results.

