4. TRIAL OBJECTIVES

Primary Objective

- To evaluate if rapid GBS testing reduces maternal and neonatal antibiotic usage compared with usual care where intrapartum antibiotic prophylaxis is directed based on maternal risk factors alone, in a cluster randomised trial
- 2. To establish the real time accuracy of the Cepheid GeneXpert system rapid point of care test for GBS colonisation among women presenting to a labour ward with risk factors associated with GBS colonisation. The results of the Cepheid test will be compared against the reference standard of selective enrichment culture in a prospective cohort study

Secondary Objectives

- 1. To establish a standard operating procedure for use of a rapid, point-of-care test for GBS colonisation (GeneXpert) on a labour ward
- 2. To determine if the turnaround time (from taking the sample from the patient to obtaining a result) is compatible with the provision of a suitable duration of antibiotic administration to test positive mothers
- 3. To explore the impact of testing strategies on the rates of antibiotic administration to the woman with risk factors associated with GBS colonisation
- 4. To determine the cost and cost-effectiveness of rapid GBS testing for preventing EOGBS disease in babies born to women with risk factors for GBS transmission
- 5. To determine the GBS2 colonisation rate of neonates born to mothers who have risk factors associated with GBS colonisation, and to explore the rates of antibiotic administration and neonatal outcomes
- 6. To determine the antibiotic resistance profile of any GBS isolated from the rectal vaginal swab taken from the mother around or during her time of labour, and to compare this with the antibiotic resistance profile from any GBS isolated from a faecal sample taken from the woman's baby at six weeks of age
- 7. To estimate the carriage rate of three groups of antibiotic resistant bacteria of current public health concern in rectal samples from women recruited to the GBS2 study from centres in London and the South-East who are assigned a rapid test system. The groups are meticillin-resistant Staphylococcus aureus

(MRSA), vancomycin-resistant enterococci (VRE), and extended-spectrum β -lactamase producing (ES β L) Enterobacteriaceae

- 8. To confirm that there is vertical transmission of MRSA, VRE or ES β L producing Enterobacteriaceae from mothers to their infants

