Units supplied with a rapid test will be asked only to offer IAP based on the results of the rapid GBS test or if the woman specifically requests them, not the presence of maternal risk factors alone. If the rapid test is positive, the mother will be presumed to be colonised with GBS (given the anticipated high sensitivity) and offered IAP.

If the rapid test is negative, no IAP should be offered for prevention of GBS transmission, unless the women is pyrexic, suspected or confirmed to have chorioaminotitis, or directly requests antibiotic prophylaxis.

If more than 15 minutes have elapsed from when the swab was inserted into the test cartridge and the test cartridge being loaded onto the machine and analysis commenced, or the rapid test fails to deliver a result within 55 minutes of loading the sample on the machine the test will be designated as 'failed'. As the women has risk factors associated with GBS colonisation they will be given intrapartum antiobiotic prophylaxis as per the RCOG guideline. We do not anticipate that more than 10% of tests will fail to deliver a timely result.

Should more than 48 hours have elapsed since the test result has become available and the woman has still to deliver then the test result shall be regarded as invalid. In this situation the woman should be re-swabbed and the presence of GBS tested for using both the rapid test and microbiological techniques.

The use of any IAP will be collected, including information of whether IAP was declined or given the progression of the labour deemed too late to be administered. The date and time the administration of IAP was initiated will be recorded.

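### The planned accuracy estimate covers only rapid tests that gave a timely result; women with a failed test receive IAP, and the exclusion may be related to the test result

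*Protocol*

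**What the plan says.** Section 4 (Trial Objectives) gives as a primary objective "To establish the real time accuracy of the Cepheid GeneXpert system rapid point of care test for GBS colonisation", judged against enrichment culture. Statistical Considerations, Test accuracy study, states "Sample size calculations are thus based on showing a test with sensitivity of 96.4% is greater than a fixed value of 90" per cent, which needs 167 colonised women for 90% power. The total of 676 is reached "whilst allowing for 10% loss from failed tests". That leaves 606 women with data, split into 167 colonised and 439 not, and Table 1 gives its confidence intervals on exactly those two denominators. Under Analysis methods, "The accuracy of the rapid test for detection of GBS colonisation will be expressed as sensitivity, specificity, positive and negative predictive values" and likelihood ratios, with no rule for failed tests.

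Section 5 (GeneXpert rapid test platform; Antibiotic administration) defines failure. Either more than 15 minutes pass between inserting the swab in the cartridge and starting the run, or the machine has given no result 55 minutes after loading. The woman is then given IAP on account of her risk factors. The protocol adds: "We do not anticipate that more than 10% of tests will fail to deliver a timely result". The platform section gives average run times of 35 minutes for a positive result and 55 minutes for a negative one. Secondary objective 2 is "To determine if the turnaround time (from taking the sample from the patient to obtaining a result) is compatible" with adequate antibiotic cover for mothers who test positive.

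**The concern.** The objective is accuracy on the labour ward in real time, but the only estimate that the plan sizes and tabulates is conditional on the test having worked in time. A failed test has the same consequence for the woman as a positive one: she receives IAP. No accuracy measure in the protocol reflects that route, so specificity and PPV in valid tests say little about how many non-colonised women the strategy treats.

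The second issue is selection. The failure limit falls at the average run time of a negative result and 20 minutes beyond the average run time of a positive one. If run times vary around those averages, failures will fall mainly on runs heading for a negative reading. Some of those are false negatives. Removing them raises the sensitivity that is tested against 90%.

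**Working it through.** **1. Does the plan's sample size take failed tests out?** Inputs from Statistical Considerations: p0 = 0.90, p1 = 0.964, prevalence 29.8%, 10% failed. The significance level is given as "statistically significantly (with p<0.05) greater than 90" per cent, without a stated number of sides. For one proportion, normal approximation, two-sided 0.05:

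n = [(1.96·√(0.90·0.10) + z_power·√(0.964·0.036)) / 0.064]²

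This gives 166.9, so 167, at 90% power, and 135.4, so 136, at 80% power. Both match the plan. The smallest number of evaluable women with at least a 90% chance of 167 or more carriers at 29.8% prevalence is 608 (exact binomial), and 608/0.9 = 675.6, so 676. The stated total is reproduced only with the 10% removed from the accuracy denominator. (676 × 0.9 = 608, close to the stated 606.)

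**2. Accuracy as managed.** Let f be the failure rate, assumed independent of colonisation, with failures classified as treated:

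- sensitivity′ = (1 − f)·0.964 + f
- specificity′ = (1 − f)·0.989
- directed to IAP = 0.298·sensitivity′ + 0.702·(1 − specificity′)
- PPV′ = 0.298·sensitivity′ / directed to IAP

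At f = 0.10: sensitivity′ = 0.8676 + 0.10 = 0.968; specificity′ = 0.890; directed to IAP = 0.288 + 0.077 = 0.365; PPV′ = 0.789.

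| f | Sensitivity | Specificity | PPV | Directed to IAP |
|---|---|---|---|---|
| 0 (valid tests) | 96.4% | 98.9% | 97.4% | 29.5% |
| 5% | 96.6% | 94.0% | 87.2% | 33.0% |
| 10% | 96.8% | 89.0% | 78.9% | 36.5% |

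In 676 women at f = 0.10, non-colonised women treated after a failure number 676 × 0.10 × 0.702 = 47. Those treated after a false positive number 676 × 0.90 × 0.702 × 0.011 = 5. Failures are then 91% of overtreatment. This share, f / (1 − specificity′), depends on the accuracy assumed. It is 0.10/0.172 = 58% with the updated pooled PCR specificity of 92% quoted in the Introduction, and 0.10/0.217 = 46% with the GBS1 value of 87%.

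**3. Effect of informative failure on sensitivity.** The protocol gives no distribution of run times, so this is an illustration. Assume true sensitivity 90%, specificity 98.9%, and that only runs heading for a negative reading time out, a fraction t of them:

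valid-only sensitivity = 0.90 / (0.90 + 0.10·(1 − t))

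- t = 10%: 0.90/0.99 = 90.9%.
- t = 50%: 0.90/0.95 = 94.7%.

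Negative runs are 0.298·0.10 + 0.702·0.989 = 72.4% of tests, so t = 10% means 7.2% of tests fail and t = 50% means 36%. At the plan's 10% ceiling, t = 0.10/0.724 = 13.8% and valid-only sensitivity is 0.90/(0.90 + 0.0862) = 91.3%. Within the anticipated failure rate the inflation is about one percentage point under this mechanism. It becomes large only if failures run well above the ceiling.

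**The case against.** The strongest reply is that the 10% is a sample-size allowance and that the analysis text does not say failed tests are excluded. How they enter the 2x2 table could be settled in an SAP, which is not at hand. That is fair as far as the Analysis methods section goes. But the sample size, the 606 and Table 1 already fix a denominator without them. Accuracy among tests that give a result is also a legitimate quantity. The point is that it should not stand alone.

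Several stronger readings are tempting and not supported:

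- *The failure route is missing from the trial.* It is not. IAP prescription is the primary outcome, analysed by intention to treat, so IAP after a failure counts. Start time, duration and outcome are downloaded for every test, and the printout gives the reason for any failure.
- *The turnaround objective is met by construction, because accepted results come within about 70 minutes of inoculation (15 + 55).* Objective 2 concerns adequate antibiotic duration, which depends on time to delivery. Turnaround also starts at sampling, and nothing excludes failed tests from that analysis.
- *The economic model will understate the number treated.* The Economic analysis section says the accuracy data will "allow the treatment pathways followed by women on the basis of the tests results to be modelled", but it also takes pathway information from the cluster trial.
- *The fall in specificity exceeds the precision claimed for it (within 6%).* Going from 98.9% to 89.0% is a change of estimand, from test to strategy. It cannot be set against a confidence-interval width.

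Finally, 10% is given as a ceiling, and these women are treated for their risk factors, not because they are deemed positive.

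**Conclusion.** The point holds in a limited form. The accuracy estimate that the protocol fixes is conditional on a timely result. At the 10% ceiling, with failures independent of colonisation and the plan's own prevalence and accuracy, strategy specificity is about 10 points below valid-test specificity, PPV about 18 points lower, and 7 more women per 100 are directed to IAP. At 5% failures the specificity gap is about 5 points. These shifts depend on the failure rate, and the share of overtreatment due to failures depends on the true accuracy of the test.

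That the exclusion is informative is plausible rather than shown. It rests on variation in run times around the stated averages, which the protocol does not describe. The direction favours passing the 90% benchmark. The 55-minute failure limit and the 55-minute average for a negative result must be reconciled in any case.

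**What to change.** In Analysis methods, Test accuracy study, keep the analysis of valid results as the basis for the test against 90%, and add beside it:

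- the failure rate with its confidence interval, overall and by culture status;
- a sensitivity analysis using every positive or negative machine reading, whatever its timing;
- a 2x2 table in all swabbed women with a culture result, with failed tests classified as managed (IAP given). Label it strategy accuracy, and do not use it for the 90% test, because counting failures as positive raises sensitivity.

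For secondary objective 2, report the proportion of swabbed women with no usable result alongside turnaround. Reconcile the failure limit in Antibiotic administration with the run times in GeneXpert rapid test platform.

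The cost is a paragraph of wording and some extra tables. The test outcomes, times, failure reasons and culture results are already collected. The small downside is that a less favourable specificity and PPV will appear next to the headline figures.
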